- Additional editorial and grammatical updates throughout the protocol for clarity.

Protocol Amendment No. 1, dated 28 January 2022

The original Clinical Study Protocol (CSP) dated 21 September 2021 was amended to provide clarifications to some inclusion and exclusion criteria and to include new Adverse Events of Special Interest (AESI).

The following sections of the protocol have been changed:

- Synopsis, Investigators and Study Administrative Structure: Text regarding Principal Investigator removed as there is no lead Principal Investigator in this study.
- Synopsis, Section [3.1](#), [Table 3-1](#), Section [4.1.1](#): The requirement for participants to be non-vaccinated or fully vaccinated against SARS-CoV-2 was updated to state non-vaccinated or vaccinated. Stratification by anti-SARS-CoV-2 vaccination status at randomization was also updated to state non-vaccinated or vaccinated with added clarification for vaccinated status to mean having received one or more locally approved/authorized COVID-19 vaccine doses.
- Synopsis (Targeted Study Population), [Table 3-1](#), [Table 3-2](#), Section [4.1.1](#): Number of days between last vaccine dose against SARS-CoV-2 infection received and IMP administration updated to at least 14 calendar days.
- Synopsis (Targeted Study Population), [Table 3-2](#), Section [4.1.2](#): Text updated to specify that vaccination status will be documented throughout the study in the eCRF.
- Synopsis (Targeted Study Population), [Table 3-1](#), Section [4.1.1](#): Text regarding the requirement for non-vaccinated participants against SARS-CoV-2 infection to have negative results for a serology test within 2 weeks prior to randomization has been removed.
- List of Abbreviations: CDC added to list of abbreviations.
- Section [1.1](#): Omicron variant added to list of SARS-CoV variants.
- [Figure 3-1](#): Figure updated to correct a typographical error in the visits numbering.

- **Table 3-1:** Removed SARS-CoV-2 RT-PCR assessment from screening and added SARS-CoV-2 RT-PCR assessment under Day 1 with the clarification that SARS-CoV-2 RT-PCR test should be taken \leq 3 days before Day 1 and if a documented SARS-CoV-2 RT-PCR test is not available at screening, a rapid SARS-CoV-2 antigen test will be performed on the day of randomization, pre-dose (for screening criteria). Footnote h updated with this clarification and to state that either test must be negative before dosing.

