- **Table 3-1, Section 6.3.2.8:** Removed screening SARS-CoV-2 serology as an assessment.
- **Table 3-1:** Footnote b updated to include text regarding repeat of serum chemistry, hematology and coagulation being allowed once during Screening period, if values at Screening visit were outside of reference range and documented as not clinically significant.
- Section 4.1.1: Inclusion criterion 4 updated to documented negative results of a SARS-CoV-2 RT-PCR test collected \leq 3 days prior to IMP dose administration (Day 1) or a negative rapid SARS-CoV-2 antigen test on Day 1 (pre-dose). NOTE was also updated to allow participants who do not meet this criterion to be re-screened more than once and up to a maximum of two times as per investigator discretion but with prior approval of the Medical Monitor.
- Section 4.1.2: Exclusion criterion 5 updated to remove history of laboratory confirmed SARS-CoV-2 infection and to clarify SARS-CoV-2 result can be based on available data at screening or at Day 1.
- Section 4.1.2: Exclusion criterion 11 updated to list cotinine, to be consistent with section 6.2.
- Section 4.1.2: Exclusion criterion 19 updated to include text regarding use of routine vaccines.
- Section 4.1.2: Exclusion criterion 28 added.
- Section 5.1: Text regarding re-screening removed.
- Section 5.1.1: Renamed to Re-screening and added guidance on requirements and procedures for re-screening.
- Section 5.1.2: Moved text from section 5.1.1: Procedures for Randomization under this section.

- **Table 5-3:** Text added to clarify that routine vaccines are permitted if administered at least 14 days prior to Day 1 dosing or > 30 days after IMP dose.
- Section **5.4.5:** Text updated to clarify that if a participant experiences an immediate hypersensitivity reaction after receipt of the first IM injection, but before the second IM injection, further IMP should not be given.
- Section **5.4.5:** Text updated to clarify that water and food will be allowed ad libitum from 1 hour after the start of dosing.
- Section **5.4.6:** Text added to provide guidance on the size and length of the needle commonly used for IM injections.
- Section **5.4.6.1:** Text updated to clarify that co-formulated AZD7442 should be administered as a single 2 mL IM injection.
- Section **6.3.1.3:** Cardiac ischemia, cardiac failure and thrombotic events added as AESIs.
- Section **6.3.2.8:** Added rapid SARS-CoV-2 antigen test to list of SARS-CoV-2 tests.

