2.2. Secondary Objectives

Table 2-2 Secondary Objectives and Outcome Measures

Secondary Objectives	Outcome Measures

To examine the serum PK profiles of AZD7442 when administered as a single IM dose (co-formulation) (AZD8895 + AZD1061) and as two separate IM doses (AZD8895 and then AZD1061) (clonal cell line or cell pool material) of the individual mAbs in healthy adult participants	
T_{max}, AUC_{0-31d}, AUC_{0-61d}, AUC_{0-91d}, AUC_{0-181d}, t_{last}, t_{½λz}, CL/F, and V_z/F

Secondary Objectives	Outcome Measures

 To further assess the safety of AZD7442 when administered as a single IM dose (co-formulation) (AZD8895 + AZD1061) and two separate IM doses (AZD8895 and then AZD1061) (clonal cell line or cell pool material) of the individual mAbs in healthy adult participants 	
 AEs including serious AEs and AEs of special interest Laboratory assessments (hematology, clinical chemistry, and urinalysis) Physical examination Electrocardiogram Vital signs (systolic and diastolic blood pressure, pulse rate)

 To evaluate the ADA responses to AZD7442 in serum following administration a single IM dose as a co-formulation (AZD8895 + AZD1061) and as two separate IM doses (AZD8895 and then AZD1061) (clonal cell line or cell pool material) of the individual mAbs in healthy adult participants 	
 Incidence and titers of anti-AZD8895 and anti-AZD1061 antibodies

Abbreviations: AE: adverse events; AUC: area under the serum concentration-time curve; CL/F: apparent clearance after extravascular administration; IM: intramuscular; PK: pharmacokinetic; $t_{1/2}\lambda_z$: terminal elimination half-life; tlast: time of last quantifiable concentration; Tmax: time to maximum observed serum concentration; Vz/F: volume of distribution based on terminal phase after extravascular administration.

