6.3.1.3. Adverse Events of Special Interest

Adverse events of special interest are events of scientific and medical interest, specific to the further understanding of the study intervention safety profile and require close monitoring and rapid communication by the investigators to the sponsor. An AESI can be serious or non-serious. All AESIs will be recorded in the eCRF. Serious AESIs will be recorded and reported as per Section [6.3.1.6](#). See also the AZD7442 IB for additional information on AESIs.

The AESIs for AZD7442 are:

- Anaphylaxis and other serious hypersensitivity reactions, including immune complex disease
- Injection site reactions
- Cardiac ischemia, cardiac failure, and thrombotic events

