SOC	System organ class
$t_{1/2\lambda_z}$	Half-life associated with terminal slope (λ_z) of a semilogarithmic concentrationtime curve
tlast	time of last quantifiable concentration
TLFs	Tables, listings, figures
Tmax	time to maximum observed serum concentration
ULOQ	Upper Limit of Quantification

Parexel International

AstraZeneca

D8850C00009

Statistical Analysis Plan

Abbreviation or special term	Explanation
Vz/F	volume of distribution based on terminal phase after extravascular administration

AMENDMENT HISTORY

Date	Brief description of change
07 Dec 2021	Initial approved SAP
10 Mar 2022	“Fully Vaccinated” changed to “Vaccinated” Added SoC to the description of adverse events causality summary
08 Jul 2022	Removal of IA
26 Jul 2023	Addition of text for sensitivity analysis
27 Oct 2023	Added text to Section 4.14 for additional statistical analysis and corresponding forest plot figures. Minor updates throughout text.

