1 INTRODUCTION

This statistical analysis plan (SAP) documents the variables to be analysed and the statistical methods of the planned analyses and outlines the statistical programming specifications for the tables, figures and listings (TFLs). Any deviations after database lock, reasons for such deviations and all alternative or additional statistical analyses that may be performed, will be described in an SAP addendum and discussed in the Clinical Study Report (CSR). Any changes to this SAP prior to database lock will be described in a new version of the SAP.

The analyses described in this SAP are based upon the following study documents:

- Clinical Study Protocol (CSP), Version 1.0 (September 21, 2021)

The content of this SAP is compatible with the International Council for Harmonization (ICH)/Food and Drug Administration (FDA) E9 Guidance documents.

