4.11.2 Adverse Events

AEs and SAEs will be collected throughout the study from date of informed consent until the end of the follow-up. MedDRA (using the latest or current MedDRA version) will be used to code the AEs.

Adverse events with onset (start date/time) after dosing will be summarized by treatment group (dose level or administration process of AZD7442, Total AZD7442). Tabulations will include causality (related, not related) and severity (mild, moderate and severe). All tabulations will be presented by MedDRA SOC and PT with the exception of the severity tables, which will be presented by PT only. Furthermore, listings of SAE and AEs that led to withdrawal will be made and the number of participants who had any AE, SAEs, and discontinuation events will be summarized. Adverse Events of Special Interest (related to Anaphylaxis and other serious hypersensitivity reactions, and injections site reactions) will be listed and summarized. The AEs that occur before dosing will be excluded from the summary tables.

Adverse events will be listed by each dose of AZD7442. The following information will be included in the listings: verbatim term, MedDRA SOC, PT and lowest level term, start date/time, end date/time, time from last dose, causality, action taken, whether the AE was classified as serious and the outcome.

All tabulations will include the number and percentage of participants.

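### The SAP's AESI listing and summary cover two of the protocol's three AESI groups; cardiac ischemia, cardiac failure and thrombotic events are left out

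*SAP*

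**What the plan says.** Protocol Section 6.3.1.3 lists the AESIs for AZD7442 in three groups: anaphylaxis and other serious hypersensitivity reactions (with immune complex disease included), injection site reactions, and "Cardiac ischemia, cardiac failure, and thrombotic events". It notes that an AESI may be serious or non-serious, and adds: "All AESIs will be recorded in the eCRF".

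Protocol Table 2-2 makes AESIs an outcome measure of the secondary safety objective: "AEs including serious AEs and AEs of special interest". SAP Section 2.2 repeats this endpoint without limiting it to particular groups.

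The analysis commitment is in SAP Section 4.11.2: "Adverse Events of Special Interest (related to Anaphylaxis and other serious hypersensitivity reactions, and injections site reactions) will be listed and summarized". The protocol's own adverse event analysis text (Sections 10.1.1 and 11.2.5) plans no AESI output.

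**The concern.** The parenthesis in SAP 4.11.2 sets the scope of the AESI output and names only two groups. A programmer following it would produce an AESI table and listing with no cardiac or thrombotic category.

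AESIs are singled out in advance so that each group can be seen as a whole, by arm. Leaving one group out means that a named secondary outcome measure is only partly delivered. SAP Section 4.14 repeats planned analyses, safety included, without sites 7808 and 7809, so any AESI output repeated there would have the same gap.

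**Working it through.** No power, sample size or effect estimate is involved. The check compares the current protocol text with the current SAP text.

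**Scope**

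| AESI group in Protocol 6.3.1.3 | Named in SAP 4.11.2? |
|---|---|
| Anaphylaxis and other serious hypersensitivity, with immune complex disease | Yes, without the words on immune complex disease |
| Injection site reactions | Yes |
| Cardiac ischemia, cardiac failure, thrombotic events | No |

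Count: 3 groups defined − 2 named = 1 omitted.

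**Is the group picked up elsewhere?** No other SAP section names it. Section 4.14, which is where changes to protocol-planned analyses are declared, does not mention narrowing the AESIs.

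**Could the parenthesis be only an example?** It contains no eg or including, although the SAP uses eg elsewhere (Sections 4.10.4 and 4.11.5). The natural reading is that it is the complete list.

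**Timing.** The amendment log is used here only to date the addition. The entry "Cardiac ischemia, cardiac failure and thrombotic events added as AESIs" stands under "Protocol Amendment No. 1, dated 28 January 2022". The SAP amendment history gives four later revisions:

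| SAP revision | Days after 28 Jan 2022 |
|---|---|
| 10 Mar 2022 | 41 |
| 8 Jul 2022 | 41 + 120 = 161 |
| 26 Jul 2023 | 161 + 383 = 544 |
| 27 Oct 2023 | 544 + 93 = 637 |

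The 10 March 2022 revision took up the change from fully vaccinated to vaccinated, which was also part of Amendment 1. It edited the adverse event text too: "Added SoC to the description of adverse events causality summary". The AESI parenthesis stayed at two groups. SAP Section 1 still gives protocol Version 1.0 of 21 September 2021 as its basis, a version that predates the third group. This pattern suggests an oversight rather than a choice, though the documents do not state the cause.

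**What the remaining outputs provide.** Under SAP 4.11 and 4.11.2, cardiac and thrombotic events still enter the safety listings. If they start after dosing, they also enter the tables by system organ class and preferred term. Those tables count participants term by term and class by class. They do not give the number and percentage of participants in each arm with at least one event in the AESI group. The serious adverse event listing does not fill the gap, because an AESI may be non-serious.

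**The case against.** The strongest reply is that nothing goes unreported. SAP 4.11 puts all safety data in listings by treatment group, the protocol requires every AESI to be recorded in the eCRF, and events after dosing are tabulated with numbers and percentages. Only a dedicated grouping is missing. This stands, and it limits the consequence. It does not make the AESI output complete.

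A second reply is that the table, listing and figure shells may already include the third group. They are not among the documents, so what was actually programmed cannot be established. But SAP 4.2 leaves to the shells only the requirements not set elsewhere, and the AESI scope is set in the SAP itself. If the shells do include the group, the SAP text still needs to be reconciled with them. The effect on the sensitivity analysis is likewise conditional, because Section 4.14 does not mention AESIs by name.

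A third reply is that the SAP endpoint in Section 2.2 is unrestricted, so the parenthesis may simply be outdated. That is probably how the mismatch arose, and it is a reason to correct the text.

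Two smaller points are fair. The day counts measure how long the mismatch persisted, not any effect on results. The missing words on immune complex disease are editorial, since the broader hypersensitivity term can be read to cover them.

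**Conclusion.** The concern holds. The current SAP specifies an AESI listing and summary that omit one of the three groups in the current protocol, and the omission is not declared as a change. It should be corrected, but the consequence is small: no data are lost, the pharmacokinetic comparability conclusions are unaffected, and individual events remain visible in other outputs. The documents give no event rate, so no number of affected events can be stated. The conclusion rests on reading the parenthesis as exhaustive and on the SAP text alone, without sight of the shells.

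**What to change.** In SAP 4.11.2, add the third AESI group from Protocol 6.3.1.3. List its events and summarize the number and percentage of participants with any such event by treatment group. Set the terms that make up the group before the tables are run; in an open-label study, a grouping chosen afterwards would be open to challenge. Carry the category into any AESI output repeated under Section 4.14.

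At the same time, align the wording of the first group with the protocol and update the protocol version cited in SAP Section 1. Before database lock, this goes into a new SAP version; after lock, Section 1 provides for an SAP addendum with discussion in the clinical study report.

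The cost is one line of SAP text, a short list of terms, and one more category in an output already planned, repeated in the sensitivity set where applicable. No new data are needed: adverse events are MedDRA-coded and AESIs are recorded in the eCRF.

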4.11.3 Vital Signs

The results of the vital signs measurements will be listed by participant and time point including the date/time of the assessment, changes from baseline, repeat/unscheduled measurements and clinical significance. The baseline for vital signs measurements will be the pre-dose assessment on Day 1. Descriptive statistics will be presented by treatment group and time point for both observed values and changes from baseline, which will exclude unscheduled assessments. The number and percentage of participants with a clinically significant vital sign result will be tabulated by parameter.

4.11.4 Resting 12-lead Electrocardiogram

12-lead ECG results will be listed for each participant with interpretation by the investigator as “Normal”, “Abnormal CS” (clinically significant) or “Abnormal NCS” (not clinically significant). Descriptive statistics will be presented by treatment group and time point for both observed values and changes from baseline. The number and percentage of participants who meet the following conditions for QTc and QTcF will be tabulated by treatment group: >450 msec, >480 msec, >500 msec, >30 msec increase from baseline, and >60 msec increase from baseline. The shift from baseline Overall ECG Evaluation to worst Overall ECG evaluation will be tabulated for each treatment group.

Since triplicate ECGs will be performed for this study, the mean of the 3 measurements collected on a visit will be used in the by-visit summaries for that visit, but the highest of the 3 measurements collected at baseline and the highest among all post-baseline measurements will be used for the shift from baseline summaries.

4.11.5 Laboratory assessments

Hematology and clinical chemistry values will be listed by participant and time point including changes from baseline and repeat/unscheduled measurements. Summary tabulations will be presented by treatment group, which will exclude unscheduled measurements. The baseline for the measurements will be the pre-dose assessment on Day 1. Shift tables will also be presented, and will consider unscheduled assessments.

The listings will include the following information: test name, date of measurement, reference range, result and flags for any measurements that are outside the reference range (eg, AstraZeneca, program, or laboratory ranges). Clinical laboratory data will be reported in System International units in the CSR.

Additional listings will be presented for the following:

- Urinalysis (macroscopic and microscopic, if applicable)
- Pregnancy testing (including FSH)
- The results of viral serology and the drugs of abuse and alcohol screen will not be listed in the CSR.

4.11.6 Physical Examinations

The baseline/screening results of the physical examination will be documented in medical history for each participant.

Any new or aggravated clinically relevant abnormal medical physical examination finding compared to the baseline assessment will be reported as an AE.

4.11.7 Injection Site Reaction

Results of the injection site reaction assessment (including assessment of size, redness/erythema, swelling, itching/pruritus, pain or tenderness, induration, discoloration) will be listed by treatment group and participant.

4.11.8 COVID-19 Symptoms

Protocol defined COVID-19 symptoms reported during the study will be summarized by treatment group, and will be listed.

4.12 Determination of Sample Size

Preliminary analysis of PK data from the first-in-human study, D8850C00001, indicated that after an IM dose of IMP (separate AZD8895 and then AZD1061 doses) at a dose of 300 mg total protein, the CV% for Cmax of the individual mAbs, AZD8895 and AZD1061 were 35.6% and 38.5%, respectively, while the CV% for AUCs of both individual mAbs, AZD8895 and AZD1061 were < 36.4%. Therefore, assuming a mean ratio of 1 between comparators, 69 participants per group will provide at least 95% power to demonstrate comparability (90% CI contained within 0.8 and 1.25).

4.13 Interim Analysis

There will be no interim analyses in the study.

4.14 Changes to Protocol-planned Analyses

During scheduled audits of the sites #7808 and #7809, irregularities and critical findings were observed regarding collection and handling of study data. A subsequent FDA inspection also had several critical findings for data quality at these sites. Hence a sensitivity analysis is deemed necessary to analyze the robustness of the primary analysis of the trial. The sensitivity analysis will be performed on the primary and secondary endpoints including safety data and ADA endpoints.

The sensitivity analysis will be performed on the primary PK endpoints evaluating the comparability between the three treatment arms. Secondary PK endpoints, safety and ADA endpoints will also be analyzed. Demographic summary tables (excluding site #7808 and #7809) will be produced to provide details for the sensitivity analysis.

The sensitivity analysis will repeat planned analyses of the above-mentioned endpoints by excluding the sites: #7808 and #7809 to provide evidence for the robustness of the primary analysis, which include all sites (including sites: #7808 and #7809). A complete list of repeated analyses will be included in the TFL shells.

Additional PK analysis of AUC_{inf}, AUCl_{ast} and C_{max} similar to that described in Section 4.10.4 will be performed for specified subgroups of lateral thigh group, gluteal dorsal group and gluteal ventral group for each compound AZD8895, AZD1061 and AZD7442.

Further subgroup analysis will be performed by injection site within treatment group, by vaccination status within treatment group, and by body weight category within treatment group for each compound AZD8895, AZD1061 and AZD7442.

The mixed model specifications will be described in the footnotes of each subgroup analysis table.

Forest plots of the additional comparisons will present the geometric mean ratio point estimate and corresponding 90% CI. These will include the injection site vaccination status, and body weight category subgroup comparisons grouped by treatment.

Approval Signatures

Document Name: Statistical Analysis Plan 27 Oct 2023 D8850C00009

Document Number: VV-TMF-4986002

Parexel Version Number:

System Version Number: 5 .0

Document Approvals		
Reason for signing: Approved	Name: PPD	Role: PPD
Reason for signing: Approved	Name: PPD	Role: PPD

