11. STATISTICAL METHODS AND SAMPLE SIZE DETERMINATION

11.1. Description of Analysis Sets

11.1.1. General Principles

A separate SAP will be compiled for this study. The details of the formal hypothesis testing will be detailed in the SAP.

Regarding PK comparability, if the 90% CIs for the geometric mean ratios for both AUCinf (AUClast for some agencies) and Cmax are entirely contained within 0.8000 and 1.2500 for all comparisons according to the study objectives, it may be concluded that the 2 formulations (the co-formulation and the formulation from the individual vials) are comparable and the 2 materials (clonal cell line material and cell pool material) are comparable.

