4.6.2 Protocol Deviations

Important protocol deviations are defined as those deviations from the protocol likely to have an impact on the perceived efficacy and/or safety of study treatments. A full list of protocol deviations can be found in the study-specific Protocol Deviation Specification.

Deviations from the protocol will be assessed as “important” or “not-important” during a data review meeting prior to database lock. Important deviations from the protocol may lead to the exclusion of participants or data from the PKS. Deviations will be assessed before database lock.

Important deviations will include the following at a minimum:

- Violation of key inclusion and/or exclusion criteria
- Administration of prohibited concomitant medications that are expected to influence the measurement of the primary endpoint.
- Dosing deviations that are expected to influence the measurement of the primary endpoint.
- Time window deviations for safety and/or PK assessments
- Other procedural and study conduct deviations recorded by the study Clinical Unit on a protocol deviation log

All important protocol deviations will be listed.

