4.10.4 Primary Endpoint

The primary endpoints for evaluation of pharmacokinetic comparability will be assessed using a linear fixed effects analysis of variance model with the natural logarithm of primary PK parameters (eg, AUCinf [for final analysis only], AUClast, Cmax and AUC0-91d [for IA only]) for the individual mAbs AZD8895 and AZD1061, as well as for the sum of the individual mAbs of AZD7442 (AZD8895 + AZD1061) as the response variables, treatment, injection site, anti-COVID-19 vaccination status (as reported on the CRF), and continuous baseline body weight on the log scale as fixed effects and participant as a random effect.

Transformed back from the logarithmic scale, geometric least square means (GLSM) together with CIs (2-sided 95%) will be estimated and presented by treatment. Also, ratios of geometric least square means together with CIs (2-sided 90%) will be estimated and presented.

The following treatment comparisons will apply:

- Treatment A vs Treatment B
- Treatment A vs Treatment C
- Treatment B vs Treatment C

where:

- Treatment A: 300 mg (total protein) AZD7442 as a single IM dose (co-formulation of 150 mg AZD8895 + 150 mg AZD1061) (clonal cell line material).

- Treatment B: 300 mg (total protein) AZD7442 as two separate IM doses of the individual mAbs (150 mg AZD8895 and then 150 mg AZD1061) (clonal cell line material).
- Treatment C: 300 mg (total protein) AZD7442 as two separate IM doses of the individual mAbs (150 mg AZD8895 and then 150 mg AZD1061) (cell pool material).

One statistical model will be fitted for each PK parameter, including all study data. Estimating parameters for the comparisons listed above will be done from this one model making use of the appropriate contrasts.

A variance component covariance structure will be used for the within-participant errors. Degrees of freedom will be determined using Kenward-Roger approximation.

If the estimating algorithms do not converge, these covariance structures will be tried: first-order autoregressive, compound symmetry, unstructured and Toeplitz.

Missing values will not be imputed. In this analysis it is thus assumed that any missing values are missing at random (MAR).

The following figures, in black and white, will be generated:

Figure	Analysis set	Presented by

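### Does dropping sites #7808 and #7809 in a simple repeat analysis leave the robustness question in SAP 4.14 unanswerable?

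*SAP*

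**What the plan says.** SAP 4.14 reports irregularities found at sponsor-side audits of the two sites and adds that "A subsequent FDA inspection also had several critical findings for data quality at these sites". Its response is an exclusion analysis: "The sensitivity analysis will repeat planned analyses of the above-mentioned endpoints by excluding the sites: #7808 and #7809". This covers primary and secondary PK, safety and ADA endpoints, with demographic tables for the reduced set. The purpose is given as "to provide evidence for the robustness of the primary analysis, which include all sites (including sites: #7808 and #7809". On the detail, "A complete list of repeated analyses will be included in the TFL shells"; those shells are not among the documents reviewed.

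SAP 4.10.4 defines the primary model: "One statistical model will be fitted for each PK parameter, including all study data". Its terms are treatment, anatomical injection site, vaccination status and log body weight, with no study-center term. Protocol 11.1.1 allows a conclusion of comparability when the 90% CIs "are entirely contained within 0.8000 and 1.2500 for all comparisons according to the study objectives". SAP 4.6.2 adds a participant-level route: "Important deviations from the protocol may lead to the exclusion of participants or data from the PKS". SAP section 1 covers later edits: "Any changes to this SAP prior to database lock will be described in a new version of the SAP".

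**The concern.** Whether the two sites changed the result is a question about movement in the ratio. The comparability criterion is about CI containment, and the reduced analysis has fewer participants and so wider CIs. A reader who compares pass with pass or fail would confuse bias with lost precision. SAP 4.14 plans neither an estimate of the shift with its uncertainty nor a result for the two sites alone, and it has no sentence on what happens if the two runs disagree. The added subgroup analyses and forest plots concern anatomical injection site, vaccination status and body weight, not study center.

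Error in the other direction also matters. If records at these sites carried no treatment signal, they would pull the all-sites ratio toward 1 and favor a comparability claim. That is a scenario only, since the documents do not describe the irregularities. An interpretation chosen after both results are known would be open to challenge.

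**Working it through.** **Inputs.** 69 per arm, true ratio 1 and the CVs come from Protocol 11.4 and Table 11-1 (power statement repeated in SAP 4.12). The limits 0.80–1.25 with a 90% CI come from Protocol 11.1.1. Enrolment by site is not given, so the share of participants at the two sites is assumed to be 10%, 20%, 1/3 or 50%, equal across arms. Covariates are assumed to explain no variance.

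**The plan's own figure.** σ = √ln(1 + CV²). At CV 38.5%, σ = 0.3718. Two one-sided 5% tests with 69 per arm give power of 93.8% at CV 38.5%, 96.0% at 36.4% and 96.7% at 35.6%. The stated figure of at least 95% is reproduced to within about a point at the largest CV.

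**Loss of precision alone.** CI factor = exp(t₀.₉₅,₃ₙ₋₇ × σ × √(2/n)). For AZD1061 Cmax, with an observed GMR of 0.89 that does not move:

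| n per arm | CI factor | Lower limit |
|---|---|---|
| 69 | 1.110 | 0.89/1.110 = 0.802 |
| 62 | 1.117 | 0.797 |
| 55 | 1.125 | 0.791 |
| 46 | 1.137 | 0.783 |

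So a borderline pass can become a miss with no site effect. The result depends on the inputs. At the same CV, an observed GMR of 0.95 still passes at 34 per arm (factor 1.162, lower limit 0.818). At CV 26.8%, a GMR of 0.89 still passes at 46 per arm (factor 1.095, lower limit 0.813).

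**Chance that the repeat misses, given that the all-sites run passes** (true GMR 1, no site effect, one comparison, 400,000 simulated trials per cell):

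| Parameter (CV) | 10% | 20% | 1/3 | 50% |
|---|---|---|---|---|
| AZD1061 Cmax (38.5%) | 4% | 9% | 18% | 38% |
| AZD1061 AUClast (30.4%) | 0.7% | 1.8% | 5% | 14–15% |
| AZD8895 AUCinf (26.8%) | 0.1–0.2% | 0.5% | 1.6% | 6–7% |

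The ranges reflect rounding of arm sizes (half of 69 taken as 34 or 34.5) and simulation error.

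**What a formal shift estimate would add** (AZD1061 Cmax). With n_r per arm retained and n_e excluded:

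- SE of the change in log GMR = σ√(2/n_r − 2/69) = 0.021, 0.032, 0.045, 0.063. The 90% limits, exp(1.645 × SE), are ×/÷1.04, 1.05, 1.08, 1.11.
- SE of the excluded-versus-retained contrast = σ√(2/n_e + 2/n_r) = 0.211, 0.158, 0.134, 0.127. The 90% limits are ×/÷1.42, 1.30, 1.25, 1.23.

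Under these assumptions the change equals share × contrast (for example 0.5 × 0.127 = 0.063), so the tighter limits on the change carry no extra power. Suppose the excluded sites differed from the rest by a ratio of 0.80, the whole margin: |ln 0.80| = 0.223. Dividing by the contrast SE gives 1.06, 1.41, 1.66 and 1.76. The chance that the 90% CI excludes 1 on that side is Φ(ratio − 1.645), about 28%, 41%, 51% and 55%. A difference that large would be missed about half the time or more.

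**The case for a change.** The strongest case for a change is that dividing the two reported ratios gives a shift without uncertainty, and two CIs from overlapping data cannot be combined by eye. The shells are assigned a list of repeated analyses, not a rule, so they are unlikely to fill the gap. The signal-free scenario could be costly. If the true ratio at the other sites were 0.80 and the two sites contributed records with ratio 1, the all-sites ratio would be 0.80^(1 − share) = 0.82, 0.84, 0.86 or 0.89, and AZD1061 Cmax would pass about 10%, 17%, 32% or 54% of the time instead of 5%. A sentence in the SAP would cost little.

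The missing CI on the shift and the missing sentence on discordance both stand as facts. The rest does not carry the case. In that scenario the planned exclusion run is the right tool: it uses none of the questioned records, estimates the 0.80 directly and keeps its own 5% error rate at the margin. The contrast depends on those records. The two ways of expressing the shift are equivalent only with equal site shares across arms and no covariate effects, yet center is not a listed stratification factor and the model has covariates. The SE of the change also assumes equal variance in both site groups, which noisy data at the two sites would break. No threshold for the contrast suggests itself, so adding it would leave robustness a matter of judgment.

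**Conclusion.** No change is needed. SAP 4.14 calls the all-sites analysis primary and the exclusion run a sensitivity analysis, so the labels already say which result carries the conclusion. The repeat of SAP 4.10.4 gives each ratio with its 90% CI, and no text says that robustness means the reduced CI must stay within 0.80–1.25. Warning against a bare pass/fail comparison is sound advice, but the SAP does not prescribe one. This is a conventional exclusion analysis, and its readers can weigh movement of the point estimate alongside CI width.

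An added contrast would leave the analysis set, the decision criterion and the governing result as they are. Its limits of ×/÷1.23 to 1.42 would seldom settle anything.

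The 4% to 38% figure rests on the largest CV in Table 11-1, assumed site shares of 10% to 50% equal across arms, a true ratio of 1 and no variance explained by body weight. At the lowest CV it is well under 1% up to about 7%. If the two sites hold a large share of participants, a discordant AZD1061 Cmax repeat is plausible by chance alone, and the study report would need to say so. That is a matter of interpretation, not a flaw in the planned analysis.
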